Of the 34 subjects implanted with the neurostimulator, only one subject was a non-responder after 2-hours of daily stimulation. This subject was a responder after an additional 14-days at 4 hours of daily stimulation and continued into the post-trial follow-up phase. There have been twelve device explants in the trial and two subjects exited the trial without device explant (one due to lost-to-follow-up, one due to an adverse event of dementia). Eleven subjects requested explant due to therapy not producing desired effect or unsatisfied with therapy or device performance, and one subject was explanted due to non-compliance.

Phase I responders will continue to be followed until US PMA approval. European approval, CE Mark, may be achieved earlier or later than PMA approval is achieved which may be 36 months or longer post trialing period for some subjects; however, all subjects will be followed until US PMA approval. If Neuspera determines that regulatory approval will not be achieved, the trial will be closed. If regulatory approval is achieved, the subjects may be approached to continue participation in a post market clinical study and will be provided a separate informed consent at that time.

Phase I Sub-Study: There is a sub-study to investigate the effectiveness and subject acceptance of half-hour daily stimulation to treat UUI. The details are provided in Appendix A: Phase I Sub-Study.

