# 6.1.1 Analysis Populations

Intent-to-Treat (ITT) Analysis Set: The ITT analysis set is defined as all Phase II subjects who have signed informed consent. Demographic information and study exit details will be reported separately for those subjects included in the ITT population where no initial implant was attempted.

Modified Intent-to-Treat (mITT) Analysis Set: The mITT analysis set is defined as all Phase II subjects for whom an initial implant is attempted. The mITT analysis set is the primary analysis set for assessment of primary endpoints.

Implanted Analysis Set: The Implanted analysis set is defined as all Phase II subjects who are implanted with the Neuspera SNS system.

Responder Analysis Set: The Responder analysis set is defined as subjects who are implanted with the system and are defined as responders at Day 28 or Day 42 clinic visit post-implant.

Per Protocol (PP) Analysis Set: The Per Protocol analysis set is defined as implanted subjects who have no protocol deviations that may significantly affect the primary endpoints. The determination of subjects excluded from Per Protocol analysis set will be made prior to analysis.

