For the primary efficacy endpoint, subjects withdrawing for reasons related to a lack of efficacy or due to an adverse event (including death) will be counted as failures. Also, those subjects who take OAB medications (after the first two weeks following implant) and prior to the six-month visit should be adjudicated as device failures. For subjects with missing primary efficacy endpoint results for other reasons (missing diary, subject loss-to-follow-up, etc.), multiple imputation will be used to impute the outcome and results from the imputed data sets combined appropriately to preserve valid inference. Details of the multiple imputation are provided in the Statistical Analysis Plan.

The primary efficacy endpoint will be presented by study visit with descriptive statistics and nominal 95% confidence intervals.

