#### 6.3 **Analysis of Replacements, Explants**

During the course of the study, it may be necessary for the investigational device to be replaced or permanently explanted from the subject. Revision rates in the literature range from 4% in the InSite study to 33% in the Herbison study. Depending on the timing of replacements, it may be necessary for the subject's response rate to be reassessed in the first 28 to 42-days post-implant.

During Phase I of the study, if a subject receives a neurostimulator replacement prior to Month 3 clinic visit, the subject will restart their follow-up schedule, and repeat the trialing period and any of the follow-up visits completed prior to replacement. If a subject receives a device replacement prior to the assessment of the primary efficacy endpoint in Phase II (Month 6 clinic visit), the subject will restart their entire follow-up schedule post-implant, including the responder rate assessments at Day 28 and Day 42, if not a responder at Day 28. The date of replacement will be considered the new Device Implant date for analysis and follow-up purposes. If a device replacement is required after the follow-up periods indicated above, subjects will continue on their original follow-up schedule and will not repeat any of the assessments or follow-up visits already completed.

If assessment of the response rate is repeated in the first 28 to 42-days post-implant, data collected after the most recent implant will be used in the analysis. Similarly, if the subject is required to repeat any portion of the post-implant follow-up visits after a replacement (replacement occurred before Month 6 clinic visit), the data from the replacement visit(s) will be used in analysis. The date of replacement will be considered the Device Implant date for analysis and follow-up purposes. A subject is only allowed to repeat any portion of the post-implant period once.

If the device is permanently explanted prior to the assessment of the primary efficacy endpoint for any reason, the subject will be considered a failure for the primary efficacy analysis.

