#### 17 VULNERABLE POPULATION

The subject population of this clinical investigation does not meet the criteria for a vulnerable population as defined in ISO 14155, Section 3.55 and ICH-GCP, Section 1.61. If a subject loses ability to consent during the course of the clinical investigation, this will lead to study exit. Such subjects will be followed for safety for the course of the study, but their data will not be used for data analysis.

Protocol no: NSM-004; Version 21.0 Page 129 of 141 04 Apr 2025 Confidential Neuspera

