5.6.1.1 Primary Safety Analysis

There is no planned statistical hypothesis test for the primary safety endpoint. The proportion of subjects experiencing an event, as well as the numerator and denominator, and the associated two-sided exact 95% binomial confidence interval will be provided. Values will be expressed as percentages.

The primary analysis population for the primary safety endpoint is the mITT Analysis set as defined in Section 5.2. Subjects who exit the study prior to reaching the 6-month post-implant follow-up visit without experiencing a device-related SAE will be assumed free of such an event. Any adverse events reported for enrolled subjects who are excluded from mITT Analysis set will be reported separately for the duration of participation in the study.

Statistical Analysis Plan Pa			ge 15 of 25
Sponsor	Study		Version
Neuspera	Clinical Study of Neuspera's Implantable Sacral Nerve Stimulation (SNS) System in Patients with Symptoms of Urinary Urgency Incontinence (UUI)		17.0

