5.6.4 Handling of Missing Data

All attempts will be made to limit the amount of missing data. No attempt will be made to impute missing data for any analyses except for the primary and secondary efficacy endpoints as specified below in the mITT analysis set. If a data point is missing, that data point will not contribute to that portion of the analysis. The number of evaluable observations will be reported in the analysis so that extent of missing data can be assessed.

For the following efficacy endpoints, subjects withdrawing for reasons related to a lack of efficacy or due to an adverse event (including death) will be counted as failures if they do not have evaluable data for the endpoint:

- The percentage of all implanted subjects who experience an improvement in UUI symptoms of 50% or more at 6-month post-implant (primary efficacy endpoint)
- The percentage of all implanted subjects who experience an improvement in UUI symptoms of 50% or more at 12-month post-implant (secondary efficacy endpoint)

For the continuous efficacy endpoints that may be used for labeling claims, no change from baseline values will be assumed for subjects withdrawing for reasons related to a lack of efficacy or due to an adverse event (including death) if they do not have evaluable data for the endpoint.

If data on these endpoints are missing for other reasons (missing diary or ICIQ-OAB questionnaire, subject loss-to-follow-up, etc.), multiple imputation will be used to impute the outcome. Results from the imputed data sets will be combined appropriately to preserve valid inference. A tipping point analysis will also be performed, examining outcomes for the primary efficacy endpoint for all possible permutations of imputed values for missing subjects.

Multiple imputation will be based on the following variables and will use full conditional specification and 100 imputed data sets. Variables to be included in the imputation model include:

- baseline age, investigational site, baseline UUI episodes, and all available follow-up visit UUI
 episodes through 6 months or 12 months (for the primary and secondary efficacy endpoints of
 improvement in UUI)
- baseline age, investigational site, baseline score, and all available follow-up visit scores through 6 months or 12 months (for the remaining secondary efficacy endpoints that may be used for labeling claims)

S	tatistical Analysis Plan	Pa	ge 21 of 25
Sponsor	Study		Version

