5.9 Safety Analyses

Investigators are required to report all AEs during the course of the study. Investigators are responsible for providing a description of all AEs, including the date of the event, treatment and the clinical outcomes for the subject. Investigators will evaluate each event for seriousness, severity and relatedness to the procedure, device or stimulation therapy. All adverse events, including unanticipated adverse device effects (UADE), and serious adverse events (SAE) will be reported for all enrolled subjects.

For Phase I, all adverse events reported over the course of the study will be summarized for all enrolled subjects. Any adverse events reported for consented subjects who were not enrolled will be reported separately.

For Phase II, all adverse events reported over the course of the study will be summarized for the mITT analysis set. Any adverse events reported for enrolled (i.e., consented) subjects who are excluded from mITT analysis set will be reported separately.

Adverse events will be tabulated with the number of events and subjects with event for each event type and overall. Rates will be reported as the number of subjects who experience at least one event during the analysis interval out of the total number of subjects with follow-up to the beginning of the analysis interval. Serious adverse events will also be tabulated. The rate of all AEs and SAEs reported in the study will be reported.

All AEs and SAEs will also be summarized by relatedness. Adverse events leading to death or study discontinuation will be provided in a listing format.

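### Protocol Section 17 bars use of data from subjects who lose the ability to consent, with no limit by time or data type, and is not reconciled with the mITT, failure and safety rules

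*Protocol*

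**What the plan says.** Under Protocol Section 17, a subject who loses the ability to consent during the study exits it. The section continues: "Such subjects will be followed for safety for the course of the study, but their data will not be used for data analysis". It does not separate data from before and after the loss, or efficacy from safety data.

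The analysis rules contain no matching exception:

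- **Analysis set** (Protocol 6.1.1; same in SAP 5.2): "The mITT analysis set is defined as all Phase II subjects for whom an initial implant is attempted".
- **Exit for lack of efficacy or an adverse event** (Protocol 6.1.2.3; also SAP 5.6.2 and 5.6.4): "subjects withdrawing for reasons related to a lack of efficacy or due to an adverse event (including death) will be counted as failures".
- **Explant** (Protocol 6.3 and SAP 5.7): "If the device is permanently explanted prior to the assessment of the primary efficacy endpoint for any reason, the subject will be considered a failure".
- **Everything else** (SAP 5.6.4): "If data on these endpoints are missing for other reasons", the outcome is multiply imputed.
- **Primary safety** (Protocol 6.1.3.3 and SAP 5.6.1.1): subjects who leave before Month 6 "without experiencing a device-related SAE will be assumed free of such an event", so they stay in the denominator.
- **Adverse events** (SAP 5.9): "For Phase II, all adverse events reported over the course of the study will be summarized for the mITT analysis set".

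Neither Protocol Section 6 nor the SAP mentions loss of capacity or refers to Section 17.

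**The concern.** Two sets of instructions apply to the same subject, and nothing says which prevails. Membership of the mITT set is fixed at the implant attempt, and every member is assigned an efficacy outcome. Section 17, as written, removes a member because of a later event, and that event may itself be an adverse event.

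The sharpest case is loss of capacity through an adverse event before Month 6. Protocol 6.1.2.3 counts that exit as a failure; Section 17 leaves it out. If the subject loses capacity after Month 6, a recorded responder could be left out instead. On the safety side, one sentence orders follow-up and then bars its results from analysis. If the conflict is left open, the choice between the rules may be made once the subject's outcome is known.

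**Working it through.** **1. The two readings compared**

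| Item | Existing rule | Section 17, literal | Section 17, only data after capacity is lost |
|---|---|---|---|
| mITT membership | Kept (6.1.1) | Removed | Kept |
| Exit due to an AE before Month 6 | Failure (6.1.2.3) | Removed | Failure |
| Explant before Month 6 | Failure (6.3) | Removed | Failure |
| Outcome missing for another reason | Imputed (SAP 5.6.4) | Removed | Imputed |
| Safety denominator | Kept (6.1.3.3) | Removed | Kept |
| Device-related SAE found in follow-up after exit | Counted through Month 6; AEs summarized for mITT (SAP 5.9) | Not used | Not used |

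The literal reading conflicts on every row. The narrower reading conflicts only on the last.

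**2. Inputs for the efficacy illustration**

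Null 0.50 and one-sided alpha 0.025, exact binomial test (Protocol 6.1.2.3). Planned N is 120 attempted implants (Protocol 6.2). Protocol 3.1.2.2.2 and 4.4 report 130 implant-attempted subjects, taken here as the running total. The number of affected subjects is set to one as an assumption, since the documents give none for Phase II.

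Formula: p = P(X ≥ x) with X ~ Bin(n, 0.50).

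**3. The plan's own threshold**

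72/120 gives p=0.0177 and 71/120 gives p=0.0274. The stated minimum of 72 out of 120 is reproduced.

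**4. One subject dropped, literal reading only**

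| N | Subject dropped | Kept | Dropped | Verdict changes? |
|---|---|---|---|---|
| 120 | A failure, 71 responders | 71/120, p=0.0274, fail | 71/119, p=0.0216, pass | Yes, toward success |
| 120 | A responder, at the boundary | 72/120, p=0.0177, pass | 71/119, p=0.0216, pass | No |
| 130 | A failure, 76 responders | 76/130, p=0.0325, fail | 76/129, p=0.0262, fail | No |
| 130 | A responder, at the boundary | 77/130, p=0.0216, pass | 76/129, p=0.0262, fail | Yes, toward failure |

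At 129 the threshold is still 77 (77/129, p=0.0171). It is the same as at 130, so one dropped failure cannot change the verdict there.

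**5. Primary safety**

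Suppose one such subject has a device-related SAE. Clopper-Pearson 95% intervals:

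- Kept: 1/120 = 0.8% (0.02% to 4.6%).
- Dropped, literal reading: 0/119 = 0% (0% to 3.1%).
- Subject kept but SAE not used, narrower reading: 0/120 = 0% (0% to 3.0%).

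This is hypothetical: Protocol 3.1.2.2.2 reports no serious adverse device effects to date.

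**6. Frequency**

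The only related observation is in the Protocol synopsis, Phase I: "two subjects exited the trial without device explant (one due to lost-to-follow-up, one due to an adverse event of dementia"). That exit is undated, is not stated to be a loss of the ability to consent, and lies outside the Phase II mITT set. No rate for Phase II follows from it.

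**The case against.** The strongest reply is that Section 17 is a consent provision, not an analysis-set definition. The sets and outcome rules live in Protocol Section 6 and the SAP, which already give these subjects an outcome. The sentence contrasts follow-up after exit with data analysis, so it can naturally mean only data gathered after exit. This is a fair reading, and on it the efficacy analysis is intact. But the text does not say so, and the safety conflict in the same sentence remains.

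On safety, adjudication by the Clinical Events Committee is decisive for safety endpoints (Protocol 8.2.1 and 12.4), and SAP 5.9 summarizes all adverse events for the mITT set. A reader might infer that the event-free assumption would overwrite a recorded SAE. The documents do not support that: the assumption applies only to subjects who had no such event. The difficulty comes from Section 17 barring use of the record.

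A reader might also infer that the clause favours the device by removing failures. That holds for one failure at exactly 71 responders out of 120. At 130 a single exclusion can only make success harder. Nor does the Phase I dementia exit support an expected number of Phase II cases.

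Finally, SAP Section 6 allows an amended SAP or a justification in the study report, and SAP 5.3 reports exclusions with reasons. Any exclusion would therefore be visible. An SAP change alone would still leave the protocol clause contradicting it.

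**Conclusion.** The point holds as a contradiction between stated rules. On the literal reading, Section 17 overrides the mITT set and the outcome rules for efficacy and safety. On the narrower reading, only safety findings after capacity is lost are affected. The documents do not say which reading applies.

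The practical size is probably small. Few subjects are likely to be affected, though this is a judgement because no usable frequency is given. A single exclusion changes the efficacy verdict only at the boundary, in a direction that depends on N and on whether the subject is a failure or a responder. The safety proportion could change by one event, about 0.8 percentage points at 120. These figures assume one affected subject, complete outcomes for the others, and 130 as the running total of attempts.

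It is worth correcting because the remedy is cheap and removes a choice that might otherwise be made with the outcome in view.

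**What to change.** Replace the last clause of Section 17 with wording to this effect:

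- These subjects stay in the mITT set for efficacy and safety.
- Data collected under valid consent are analysed.
- The primary efficacy outcome follows Protocol 6.1.2.3 and 6.3 and SAP 5.6.4 and 5.7.
- Safety data collected after exit are included where consent and local rules permit.

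Add a cross-reference in SAP 5.6.4 saying that its rules apply to Section 17 exits. Add one in SAP 5.6.1.1 saying that the event-free assumption does not displace a device-related SAE recorded in follow-up after exit, through Month 6, where its use is permitted.

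Check the wording first against the consent form, which is not in the reviewed text. If the form limits use, keep and name that limit, and report the number of subjects affected in the SAP 5.3 disposition.

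The cost is a short wording amendment, with sponsor and IRB/EC approval before implementation (Protocol 14.1), and two SAP cross-references. It needs no new data, visits or subjects, and the failure and imputation rules stay as they are.

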#### REVISION HISTORY

Version	Date	Summary of Changes/ Affected Sections
01	04 April 2025	Initial release

#### SYNOPSIS

Addendum to the SANS-UUI Study Protocol:
Phase I Sub-Study to Assess Benefit of Half-Hour Daily Stimulation
Clinical Study of Neuspera's Implantable Sacral Nerve Stimulation (SNS) System in
Patients with Symptoms of Urinary Urgency Incontinence
SANS-UUI
NSM-004
Neuspera's Implantable Sacral Nerve Stimulation (SNS) System
Miniature wireless midfield powered implanted neurostimulation device for
urinary urgency incontinence (UUI).
Neuspera's Implantable SNS System is indicated to treat subjects with UUI who
have failed or could not tolerate more conservative treatments.
Neuspera Medical Inc.
Neuspera Medical Inc.
[name]
[name], USA
[contact]
Phase I centers selected by the Sponsor based on interest and ability to complete
the sub-study in acceptable timeframe.
To determine if stimulating a half-hour per day is effective and acceptable by
subjects.
Prospective, multi-center, single-arm study with subjects acting as their own
control.
Subjects who are currently responders (50% or greater reduction in UUI from
baseline) with 2 hours daily stimulation on their most recent study visit will
complete a sub-study baseline 72-hour bladder dairy. They will then be asked to
reduce to a half-hour daily stimulation for a two-week period. At the end of two
weeks, they will complete the 72-hour bladder diary and answer two self-
assessment questions, indicating if their therapy was effective and if they are willing to continue with half-hour daily stimulation for another two weeks. This
will be repeated for two more weeks (6 weeks total) at which time subjects will
exit the sub-study. At the end of the sub-study, subjects will decide which
duration of daily stimulation is preferred to use going forward (half-hour or 2
hours).
After completing a baseline 72-hour bladder diary, there will be three sub-study
visits completed at two-week internals (14 days +/-4). Visits may be completed by telephone or in clinic.

SANS-UUI Phase I Sub-Study Addendum, version 1.0 / 04 April 2025 Confidential - Neuspera Medical Inc.

Endpoints  Safety endpoints	Assessment of subjects' satisfaction with half-hour daily simulation compared with 2 hours daily simulation.     Self-assessment of UUI symptoms     72-hour bladder diary  No additional safety endpoints in sub-study. Safety endpoint reported in SAN-
	UUI main study.
Clinical investigation popul	ation
Sample size	Up to 17 Phase I subjects currently in follow-up may participate.
Inclusion criteria	Only Phase I subjects will be eligible to participate in this study. Eligible participants should meet the following criteria:  1. Provide informed consent for this sub-study, showing their willingness to complete the additional bladder diaries, study questions, and intention to follow the daily stimulation and sub-study requirements.  2. Are responders (50% or greater reduction in UUI from baseline) at the most recent Phase I clinic visit.  3. Have demonstrated consistent use of 2 hours daily stimulation in the last 30 days before sub-study baseline bladder diary.  4. Are currently free from symptoms of urinary tract infection (UTI) or other conditions that could confound UUI symptoms before sub-study baseline bladder diary.  5. Are not experiencing any technical issues with the Neuspera system that would impact receiving stimulation.
Statistical analysis	
Statistical design	Analyses for the sub-study will consist of descriptive statistics since stand-alone definitive conclusions regarding safety or efficacy from this sub-study are not desired, and the purpose of sub-study is to inform on the feasibility of a shorter duration stimulation time. Formal statistical conclusion from this sub-study will not be made so there are no type I error concerns.

